6.2 ANALYSIS METHODS: DOR AND PFS

The date of definitive progression will be the timepoint at which progression is first identified and confirmed by the independent radiographic committee. Death following the discontinuation of study drug will be considered as an event for the DOR and PFS calculation. Data will be censored on the date of the last tumor assessment (including assessments with a Not Evaluable (NE) outcome) for patients who:

- Start alternative anti-tumor therapy prior to disease progression
- Do not have disease progression within 30 days after discontinuation of study drug(s)

TG Therapeutics, Inc. UTX-IB-301 SAP

secondary outcomes will be tested:

If the primary efficacy analysis of ORR is statistically significant for the ITT population, the following

- Complete response rate
- Duration of response
- · Time to response

For each of these outcomes, ublituximab + ibrutinib will be compared to ibrutinib. The Hochberg approach will be used to control the type I error rate. The null hypotheses state that the secondary outcomes do not differ between ublituximab + ibrutinib and ibrutinib. The three p-values associated with these three secondary outcomes are denoted p_1 , p_2 , and p_3 . The ordered p-values, from largest to smallest, are denoted $p_{(1)} \ge p_{(2)} \ge p_{(3)}$. Specifically:

- If $p_{(1)}$ is less than 0.05, all three null hypotheses will be rejected.
- Otherwise, if $p_{(2)}$ is less than 0.025, the null hypotheses associated with $p_{(2)}$ and $p_{(3)}$ will be rejected.
- Otherwise, if $p_{(3)}$ is less than 0.0167, the null hypothesis associated with $p_{(3)}$ will be rejected.

If the primary efficacy analysis of ORR is not statistically significant, the secondary efficacy variable defined above will not be formally conducted.

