6.1.2.5 PROGRESSION-FREE SURVIVAL

Progression-free survival is defined as the time from the date of randomization until the date of first documentation of definitive disease progression or date of death from any cause, whichever occurs first. Patients who die without a reported prior progression will be considered to have progressed on the day of their death. Patients who did not progress or are lost to follow-up will be censored at the day of their last tumor response assessment. If no baseline or post-baseline assessment is available, the patient will be censored at the date of randomization. If death or PD occurs after 2 or more consecutive missing tumor response assessments, censoring will occur at the date of the last response assessment prior to the missed assessments. The use of a new anticancer therapy prior to

the occurrence of PD will result in censoring at the date of last tumor response assessment prior to initiation of new therapy.

This variable will be analyzed using stratified log-rank test, and median PFS will be estimated via Kaplan-Meier methodology. PFS may not be formally analyzed at the time when the planned formal ORR analysis is conducted with approximately 120 patients who have had the opportunity to provide two efficacy assessments as it is expected that the majority of the patients from both treatment arms will not have progressed by the time of the primary ORR analysis (PFS may not be reliably estimated due to high censoring). Following the primary analysis of ORR, PFS may be analyzed at a later date. PFS will be analyzed using a stratified Cox regression model with treatment effect and stratification effect to estimate HR and 95% CI.

Censoring rules for PFS are summarized in Table 3.

TABLE 3: CENSORING RULES FOR PFS

Situation	Date of Progression or Censor	Censored/ Progressed
No baseline radiological tumor assessments	Randomization date	Censored
No post-baseline tumor assessments and no death reported before data cut-off	Randomization date	Censored
Disease progression	Date of progression	Progressed
No disease progression	Date of last tumor assessment	Censored
Treatment discontinuation for toxicity or other reasons with no disease progression per IRC	Date of last tumor assessment	Censored
Patient lost to follow-up without disease progression	Date of last tumor assessment	Censored
Death before first tumor assessment	Date of death	Progressed
Death between adequate tumor assessments	Date of death	Progressed

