Death or disease progression after ≥ 2 missed tumor assessments	Date of last tumor assessment before missed assessments or randomization date if no other tumor assessment in between	Censored
Withdrawal due to symptomatic deterioration without further tumor assessments	Date of last tumor assessment before discontinuation	Censored
Patient use of any anti-cancer therapy and/or surgery for curative intent.	Date of last tumor assessment prior to therapy or surgery, whichever occurs first	Censored
Note: Progression-free survival = date of even	t / censor – randomization date + 1	

Once the progression and survival dates are derived, PFS will be calculated as follows for patients with a PFS event:

PFS (days) = date of PD or death due to any case – randomization date + 1

(with censoring indicator = event)

For those patients who are censored for a PFS event:

[figure not shown]
PFS (days) = date of censoring – randomization date + 1

(with censoring indicator = censored)

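### SAP 6.2 makes a death after stopping study drug a PFS and DOR event, but its own 30-day rule and Table 3 censor the same death, and no rule is given precedence

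*SAP*

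**What the plan says.** Four sets of rules bear on a patient who stops study drug without progression and later dies.

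- **SAP 6.2, death sentence (DOR and PFS):** "Death following the discontinuation of study drug will be considered as an event for the DOR and PFS calculation". The sentence carries no exception.
- **SAP 6.2, next sentence (DOR and PFS):** data are censored at the last tumor assessment for two groups. One is patients who "Start alternative anti-tumor therapy prior to disease progression". The other is patients who "Do not have disease progression within 30 days after discontinuation of study drug(s".
- **SAP 6.1.2.5 and Table 3 (PFS only):** the text reads "If death or PD occurs after 2 or more consecutive missing tumor response assessments, censoring will occur", at the last assessment before the gap. Table 3 repeats this in the row "Death or disease progression after ≥ 2 missed tumor assessments". It also censors, at the last assessment, "Treatment discontinuation for toxicity or other reasons with no disease progression per IRC", and it censors for new therapy ("Patient use of any anti-cancer therapy and/or surgery for curative intent"). Other rows count a death before the first assessment, or between adequate assessments, as an event. Protocol 11.10.2.1.6 has the same missed-assessment and new-therapy rules for PFS.
- **SAP 6.1.2.2 (DOR):** death from any cause ends the response. The section gives no censoring rules, and 6.2 adds none for missed assessments.

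The SAP does not say which rule prevails. Off treatment, assessments are about every 3 months (SAP 3.1).

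**The concern.** The status of one death depends on which sentence the programmer applies. The patients concerned are foreseeable. Protocol 6.1 and SAP 3.1 follow those who stop without progression for progression and/or survival, so a death can be known after scans have lapsed. The trial is open label (SAP 3.6), so the rate of leaving drug without progression may differ by arm.

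DOR is tested by a stratified log-rank test at the two-sided 5% level. If ORR succeeds, it joins CR rate and TTR in a Hochberg procedure. If DOR has the largest of the three p-values, whether it falls below 0.05 decides whether all three hypotheses are rejected together. The event rule for such an endpoint should have one reading.

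The 30-day rule also sits badly with the follow-up schedule. With off-treatment scans about 3 months apart, progression found at a scheduled follow-up scan will usually fall more than 30 days after stopping drug, and the rule read literally would censor that as well.

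**Working it through.** The plan states no figure to reproduce here. The check applies each rule to one patient.

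**Assumed patient.** Randomized and first dosed on day 1. With 28-day cycles, the scans after cycles 2, 4 and 6 fall on days 1 + 56 = 57, 1 + 112 = 113 and 1 + 168 = 169. First PR is on day 57, the last scan on day 169, and drug is stopped on day 175. Follow-up scans due about days 169 + 91 = 260 and 260 + 91 = 351 are both missed. There is no progression and no new therapy. Death is on day 365, which is 365 − 175 = 190 days after stopping.

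**Formula.** Time = date − origin + 1. The +1 is stated for PFS (SAP 6.1.2.5) and assumed for DOR.

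| Rule applied | PFS (origin day 1) | DOR (origin day 57) |
|---|---|---|
| 6.2 death sentence | event, 365 − 1 + 1 = 365 | event, 365 − 57 + 1 = 309 |
| 6.2 30-day rule | censored, 169 − 1 + 1 = 169 | censored, 169 − 57 + 1 = 113 |
| Table 3, two or more missed | censored, 169 | no rule given |
| Table 3, discontinuation row | censored, 169 | no rule given |

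Applying Table 3 to PFS and the 6.2 death sentence to DOR gives a censored PFS time and a DOR event for the same death.

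**Missed scans are not needed for the conflict.** Take a patient who stops drug without progression, attends every follow-up scan and dies before the next one is due. Table 3's row for death between adequate assessments and the 6.2 death sentence both give an event. The 30-day rule and the discontinuation row, read literally, both give censoring.

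**New therapy.** Table 3 censors it for PFS, and the first 6.2 bullet censors it for PFS and DOR. The status agrees across endpoints.

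**Size.** The documents give no rates for discontinuation, missed scans or death, so the count cannot be derived. One simulated illustration compared only the missed-assessment rule with the death sentence. It assumed 60 patients per arm, median time to progression 36 months, 12–36 months of follow-up, half of those stopping without progression having no further scans, and mortality of 2–4% per month after stopping. About 1–3 deaths out of roughly 42–46 events changed status (1/46 = 2% to 3/42 = 7%). With no true effect on progression, monthly discontinuation of 2.0% against 0.8% and 4% mortality, the hazard ratio moved from 1.05 to 1.09. Only the shift should be read, because the absolute values depend on modeling details. The shift is ln(1.09/1.05) = 0.037, against a standard error near 2/√44 = 0.30, or about 0.12 standard errors. With equal discontinuation there was no shift. The illustration concerns PFS in all patients, not DOR in responders, and it does not cover the 30-day rule.

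**The case against.** The best defense is that 6.2 states a general rule and then its exceptions: stopping drug does not stop deaths from counting, subject to the specific censoring rules. SAP 6.1.2.5 and protocol 11.10.2.1.6 have that structure for PFS, and on missed assessments this is a reasonable reading for PFS. It is not written down, however, and it cannot settle DOR, because Table 3 does not claim to cover DOR. It also fails for the 30-day rule. A patient who progresses within 30 days already has an event at progression, and one who does not is censored. Taken literally, that exception leaves the death sentence nothing to decide.

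A second defense is that the 30-day rule censors the worked patient for both endpoints, so PFS and DOR agree. That is correct if the rule is followed. The endpoints split only if the death sentence is followed for DOR and Table 3 for PFS.

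Third, the effect may be slight. PFS is outside the Hochberg family and may be analyzed later. The date of the DOR test is not stated. If it accompanies the ORR analysis, when every patient could have reached at least 16 weeks, the last patients enrolled could not yet have missed two 3-monthly scans. Enrollment over 18–24 months means that the earliest could have. This limits the size of the problem but does not remove it.

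Finally, the public SAP shows nothing between 6.2 and the multiplicity text. A sensitivity analysis may already be specified there.

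**Conclusion.** The event and censoring rules contradict each other. For a death after discontinuation without progression, the 6.2 death sentence conflicts with the 6.2 30-day rule for both endpoints, and with Table 3's missed-assessment and discontinuation rows for PFS. The absence of a missed-assessment rule for DOR means that PFS and DOR can also disagree about the same death. This rests on the text alone; the dates in the example are assumed and serve only to show the outcomes.

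A reader might infer that new anti-cancer therapy also makes PFS and DOR diverge. It does not, since 6.2 and Table 3 both censor it. A reader might also infer that the DOR or PFS comparison is materially at risk. The documents do not support that. The number of affected deaths is not derivable and is probably small, and the illustration shows a shift of about 0.12 standard errors under unequal discontinuation and none under equal discontinuation. The reason to act is that DOR is formally tested and its event status is ambiguous.

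**What to change.** Replace the 6.2 death sentence, the two 6.2 bullets and Table 3 with one table. It should apply in stated order to PFS (origin randomization) and DOR (origin first response):

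1. New anti-tumor therapy before progression or death: censored at the last assessment before that therapy.
2. Progression or death after two or more consecutive missed assessments: censored at the last assessment before the gap, or at the origin if there is none.
3. Otherwise, IRC progression: event on that date.
4. Otherwise, death from any cause, on or off study drug: event on the date of death.
5. Alive without progression at the last assessment, including after discontinuation: censored at that assessment.

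Delete the 30-day rule. Row 5 limits the current discontinuation row to patients alive without progression; apply the same limit to the rows on withdrawal and loss to follow-up. Carry the other Table 3 rows over. Rows 1 and 2 are the existing rules of protocol 11.10.2.1.6, so PFS keeps its protocol definition.

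Unless the parts of the SAP not shown already contain it, add one sensitivity analysis of PFS and DOR that counts all deaths as events.

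The cost is SAP wording and one extra table, with no new data. It should be done before database lock, when the SAP must be final (SAP section 2).

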10.9 NON-EVALUABLE

In a patient who does not have evidence of PD, the occurrence of any of the following conditions indicates a response status of NE:

- There are no images or inadequate or missing images
- Images of the liver and spleen are missing at that time point (with the exception that absence
 of splenic images will not result in an NE designation in a patient known to have undergone
 splenectomy).

Note: A time-point will be considered to have a response of NE if any target lesion is missing. PD may be assigned at any time point regardless of the extent of missing target or non-target lesions. Missing non-target lesions will not impact the ability to assess for response or disease progression.

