3.1 STUDY DESIGN

This study is a fixed-dose, randomized, two-arm Phase 3 trial to assess the efficacy and safety of ublituximab in combination with ibrutinib compared to ibrutinib alone in patients with CLL who have received at least one prior standard treatment regimen and who have at least one high-risk cytogenetic abnormality (17p deletion, 11q deletion, and/or P53 gene mutation).

Following screening, patients meeting the inclusion/exclusion criteria will be randomized in a 1:1 ratio to one of the following treatment regimens:

- Arm A: Ublituximab + ibrutinib
- Arm B: Ibrutinib

Randomization will be stratified according to prior lines of therapy (1 prior vs. 2 or more prior lines of therapy)

All study patients will be evaluated for response after cycles 2, 4, and 6, then every 3 cycles thereafter if patient is on active treatment, or approximately every 3 months thereafter if patient is in follow up. The best clinical response as well as disease progression will be determined by an Independent Review Committee (IRC).

Patients will continue treatment until the occurrence of definitive disease progression, unacceptable toxicity, or withdrawal from the study due to investigator decision or other reasons. Patients who discontinue study treatment for reasons other than disease progression will continue to be followed for progression and/or survival approximately every 3 months.

Upon first assessment scan of the last randomized patient, and site submission of all required efficacy and safety data, the independent DSMB will review the primary and secondary efficacy analyses, and safety data.

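### Censoring PFS and DOR at a trailing Not Evaluable visit credits event-free time that no readable scan supports, though the bias is probably small

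*SAP*

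**What the plan says.** SAP Section 6.2 gives the rule for both endpoints: "Data will be censored on the date of the last tumor assessment (including assessments with a Not Evaluable (NE) outcome"). It is attached to two groups. One is patients who "Start alternative anti-tumor therapy prior to disease progression". The other is patients with no progression in the 30 days after study drug is stopped.

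Protocol Section 10.9 defines NE for a patient without evidence of progression. One condition is "There are no images or inadequate or missing images". Another is missing liver or spleen images. A note adds: "A time-point will be considered to have a response of NE if any target lesion is missing". The same note also says: "PD may be assigned at any time point regardless of the extent of missing target or non-target lesions".

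SAP Section 6.1.2.5 and its Table 3 refer to the last tumor assessment without saying whether it must be evaluable. Table 3 uses the word *adequate* in one death row and does not define it. When death or progression follows two or more missed assessments, Table 3 censors at: "Date of last tumor assessment before missed assessments or randomization date if no other tumor assessment in between". Neither document says whether an NE visit is a missed one.

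SAP Section 6.1.2.2 gives DOR no censoring rule of its own, so Section 6.2 governs it.

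**The concern.** A censoring date states that the patient was known to be event-free up to that day. At a visit with no usable images that is not known. Moving the date forward to such a visit keeps the patient in the risk set over an interval in which progression may have occurred unrecorded. That pushes the Kaplan-Meier curve up.

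DOR is the endpoint most exposed. It is tested at the two-sided 5% level and belongs to the Hochberg family that opens if ORR succeeds. PFS is estimated without a formal test in Protocol Section 11.10.2.1.6, while SAP Section 6.1.2.5 adds a stratified log-rank test and a Cox hazard ratio. The trial is open label (SAP Section 3.6), so the completeness of scans around discontinuation could differ between arms.

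**Working it through.** The documents state no event count, hazard ratio or NE rate for PFS or DOR, so there is no planned figure to reproduce. Three checks were made.

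**1. Time credited per trailing NE visit.** SAP Section 3.1: "All study patients will be evaluated for response after cycles 2, 4, and 6, then every 3 cycles thereafter". Cycles last 28 days (SAP Section 3.2), and efficacy assessments have a window of 7 days either way (Protocol Section 10).

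- Up to cycle 6: 2 x 28 = 56 days. With both visits at opposite window limits, 56 - 14 = 42 to 56 + 14 = 70 days.
- After cycle 6: 3 x 28 = 84 days, range 70 to 98 days.
- Two trailing NE visits: 112 or 168 days.

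An NE visit followed by an evaluable one adds nothing, because the later scan settles the interval.

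**2. The undefined term.** Take an evaluable scan after cycle 6, NE visits after cycles 9 and 12, and progression after cycle 15. If the NE visits are assessments, this is an event after cycle 15. If they are missed, the patient is censored after cycle 6, which is 9 x 28 = 252 days earlier. Event status depends on a word that the plan does not define.

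**3. Illustrative size.** The simulation used 12,000 patients per arm and visits at weeks 8, 16, 24, 36, 48 and so on. None of the following assumptions comes from the documents:

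- true median PFS of 104 weeks in both arms (true HR 1);
- median time to discontinuation of 104 weeks;
- cutoff between weeks 60 and 156;
- 5% NE at visits before the last.

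True week-96 PFS is 0.5^(96/104) = 0.527.

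| Chance PD is called at an NE visit | NE at last visit, arm 1 / arm 2 | Week-96 PFS, SAP rule | Week-96 PFS, last evaluable | HR, SAP rule | HR, last evaluable |
|---|---|---|---|---|---|
| 0 | 15% / 15% | 0.530 / 0.536 | 0.521 / 0.528 | 1.010 | 1.010 |
| 0 | 30% / 30% | 0.539 / 0.543 | 0.523 / 0.525 | 1.007 | 1.005 |
| 0 | 30% / 5% | 0.539 / 0.528 | 0.523 / 0.525 | 0.972 | 1.008 |
| 0.5 | 30% / 30% | 0.531 / 0.535 | 0.515 / 0.519 | 1.006 | 1.007 |
| 0.5 | 30% / 5% | 0.531 / 0.528 | 0.515 / 0.525 | 0.990 | 1.025 |
| 1 | 30% / 30% | 0.523 / 0.527 | 0.507 / 0.511 | 1.009 | 1.010 |
| 1 | 30% / 5% | 0.523 / 0.527 | 0.507 / 0.524 | 1.009 | 1.044 |

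With 5% NE in both arms and PD never called at NE visits, the SAP rule gave 0.525 and 0.532 in two identical arms. Gaps from the truth of about half a point are therefore noise. The two rules were applied to the same simulated patients, so comparisons between them are tighter.

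Where PD is never callable at an NE visit, the SAP rule is too high by 0.3 to 0.9 points at 15% NE and by 1.2 to 1.6 points at 30%, and the last-evaluable rule removes most of this. Where PD is callable half the time, the two rules bracket the truth. Where it is always callable, the SAP rule is unbiased and the last-evaluable rule reads 1.6 to 2.0 points low. The reason is that progression seen on incomplete images still counts as an event, while absence of progression at such a visit is discarded.

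The simulation applied the NE rule to every censored patient, which is wider than the two groups in Section 6.2. It did not model DOR or the missed-assessment rule.

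**The case against.** The strongest reply is that NE does not mean blind. NE is assigned only when there is no evidence of progression, and progression may be called from partial images. Protocol Section 10.8 also allows it by a new lesion, by biopsy-proven transformation, or by marrow-confirmed falls in platelets or hemoglobin. This stands. A reader might infer from Section 6.2 that progression could not be seen at any NE visit, but that is true only of visits without usable images. For partial ones it could not be ruled out.

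Three other stronger readings are tempting and not supported:

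- *That the rule covers every censored patient.* It names two groups. The second is broad, but for patients still on treatment at data cutoff Table 3 says nothing about NE.
- *That an NE visit counts as an assessment and so stops the missed-assessment rule from applying.* This is nowhere written. A visit with no images can equally be read as missed. The plan is ambiguous here, without a stated interaction.
- *That the comparison is tilted toward one arm.* Open-label treatment makes unequal scan completeness possible, but the documents give no reason to expect it, and the IRC reads blinded.

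It is also fair to say that the text between SAP Section 6.2 and the multiplicity procedure is not visible in the public copy, and that IRC reading methods sit in a separate charter. A sensitivity analysis or an NE convention may exist there. What can be said is that no visible passage overrides the rule.

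**Conclusion.** The point holds in a limited form. For the two groups in Section 6.2, censoring at a trailing NE visit adds about 56 or 84 days of event-free time that no readable scan supports. The lean is upward for PFS and DOR, and it is probably small: at most 1.2 to 1.6 points in week-96 PFS under an assumed 30% NE rate at the last visit, and nil if progression can always be called at such visits. The hazard ratio hardly moves when NE rates are equal. It moves by about 0.04 (0.972 against 1.008) under an assumed 30% versus 5% split with progression never callable. These sizes rest on assumed rates and apply to PFS. For DOR the direction carries over, but the size was not computed.

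ORR, the primary endpoint, is untouched. DOR is formally tested only if ORR succeeds. This is a correction worth making before database lock, and it poses no threat to the main conclusion.

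**What to change.** Change Section 6.2 and Table 3 together, so that both censor at the last evaluable (non-NE) IRC assessment for PFS and DOR. For PFS, fall back to the randomization date if there is no evaluable post-baseline assessment. DOR needs no such fallback, because the response itself is an evaluable assessment. Define *adequate* in Table 3 in the same terms.

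Keep the current Section 6.2 rule as a named sensitivity analysis. The simulation shows why both are needed: when progression can often be called on partial images, the last-evaluable rule leans low, and the two results then bracket the answer. Reporting trailing NE visits by arm, split into no usable images and partial images, would show which case applies.

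State whether a visit with no usable images counts as missed under the two-missed-assessments rule. Do not count partial NE visits as missed automatically: two visits each lacking one target lesion would then turn a later real progression or death into a censored observation.

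The cost is SAP wording and slightly shorter follow-up for some censored patients. No new data are needed.

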6.4 DISCONTINUATION FROM STUDY TREATMENT

Patients will be discontinued from study treatment for any of the following reasons:

- Disease progression
- Intolerable toxicity related to study drug
- Patient requests to withdraw consent or discontinue treatment
- Pregnancy
- Inability of the patient to comply with study requirements
- Conditions requiring therapeutic intervention not permitted by the protocol
- Non-compliance/lost to follow-up
- Investigator discretion
- Discontinuation of the study by the Sponsor

Patients who discontinue from study treatment (for reasons other than progressive disease) will continue to be followed for progression. **Every attempt to continue to follow the patient for progression should be made.**

After withdrawal from protocol treatment, patients should be followed for AEs for 30 calendar days after their last dose of either study drug. All new AEs occurring during this period must be reported and followed until resolution, unless, in the opinion of the investigator, these values are not likely to improve because of the underlying disease. In this case the investigators must record his or her reasoning for this decision in the patient's medical records and as a comment on the electronic Case Report Form (eCRF).

All patients who have CTCAE Grade 3 or 4 laboratory abnormalities at the time of withdrawal should be followed until the laboratory values have returned to Grade 1 or 2, unless in the opinion of the investigator, it is not likely that these values are to improve because of the underlying disease. In this

UTX-IB-301

case, the investigator must record his or her reasoning for making this decision in the patient's medical records and as a comment on the eCRF.

UTX-IB-301

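### SAP 6.2, the only censoring rule for duration of response, does not limit the censoring date to assessments before a new anti-tumor therapy, unlike the plan's own PFS rule

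*SAP*

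**What the plan says.** SAP 6.2 is headed "6.2 ANALYSIS METHODS: DOR AND PFS", so it covers both endpoints. Its rule reads "Data will be censored on the date of the last tumor assessment", with assessments rated not evaluable (NE) included, and it applies to two groups of patients. The first group is those who "Start alternative anti-tumor therapy prior to disease progression". The second is those without progression within 30 days after stopping study drug. Neither the rule nor the bullets say that the assessment must precede the new therapy.

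For PFS, the same patients are handled explicitly elsewhere:

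- SAP 6.1.2.5: use of a new anticancer therapy before "the occurrence of PD will result in censoring at the date of last tumor response assessment prior to initiation of new therapy".
- SAP Table 3, new-therapy row: "Date of last tumor assessment prior to therapy or surgery, whichever occurs first".
- Protocol 11.10.2.1.6: the same rule as SAP 6.1.2.5.

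For DOR, SAP 6.1.2.2 and Protocol 11.10.2.1.2 define the interval but give no censoring rule, and Table 3 is labelled as applying to PFS. SAP 6.1.2.2 tests DOR among ITT responders with a stratified log-rank test at the two-sided 5% level. The SAP's multiplicity text puts DOR in a Hochberg family with CR rate and time to response, tested only if ORR is significant in the ITT population.

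On follow-up, Protocol 6.4 says that patients who stop study treatment without progressive disease "will continue to be followed for progression". Protocol 6.1 and SAP 3.1 put this at about every 3 months.

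**The concern.** A programmer deriving DOR has only SAP 6.2 to work from. If a responder stops study drug, starts another agent without progression and is scanned again, the last tumor assessment on file comes after the switch. Censoring there counts disease control under another drug as duration of the study response. The plan's own PFS rule excludes that time for the same patient.

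DOR is where this matters most, because it has no other rule and carries a formal test. The trial is open label, so equal switching in the two arms cannot be assumed. If switching differs, the literal rule favors the arm that switches more.

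**Working it through.** **Step 1: Rules side by side, for a patient who starts another therapy before progression**

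| Source | Endpoint | Censoring date |
|---|---|---|
| SAP 6.1.2.5 | PFS | last assessment before the new therapy |
| SAP Table 3 | PFS | last assessment before the therapy or surgery |
| Protocol 11.10.2.1.6 | PFS | last assessment before the new therapy |
| SAP 6.2 | DOR and PFS | last assessment, no limit stated, NE included |
| SAP 6.1.2.2, Protocol 11.10.2.1.2 | DOR | none given |

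The rules give the same date only if no scan follows the switch. No section ends scanning when another therapy starts, so later scans can exist. How many there would be is unknown.

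**Step 2: One patient (assumed dates)**

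Randomized day 1; scans on days 57, 113 and 169 (ends of cycles 2, 4 and 6); first PR on day 57; other therapy from day 190 without progression. Later scans come every 84 days (3 cycles) or 91 days (3 months). The SAP's formula is PFS = date − randomization date + 1. It gives no DOR formula, so DOR = date − first response date + 1 is assumed.

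- Before-therapy rule: PFS = 169 − 1 + 1 = 169 days; DOR = 169 − 57 + 1 = 113 days.
- Literal 6.2 with one later scan, on day 169 + 84 = 253 or 169 + 91 = 260: PFS = 253 to 260; DOR = 253 − 57 + 1 = 197 to 260 − 57 + 1 = 204.

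| Later scans | PFS, before-therapy rule | PFS, literal 6.2 | DOR, before-therapy rule | DOR, literal 6.2 |
|---|---|---|---|---|
| 0 | 169 | 169 | 113 | 113 |
| 1 | 169 | 253–260 | 113 | 197–204 |
| 2 | 169 | 337–351 | 113 | 281–295 |
| 4 | 169 | 505–533 | 113 | 449–477 |

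**Step 3: Effect on the DOR comparison (simulation)**

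The documents give no switching rates, so every input here is an assumption: 45 versus 40 responders, exponential DOR with median 24 months in both arms (true hazard ratio 1, true 24-month value 0.50), 3-monthly scans, 12–36 months of follow-up, and no progression scored after switching. Each switcher gains about 14–15 months of event-free time. Ranges are across repeated runs.

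| Switching, Arm A vs B | Arm A 24-month DOR, before-therapy → literal | Hazard ratio, before-therapy → literal |
|---|---|---|
| 8% vs 8% | 0.49–0.50 → 0.52–0.53 | about 1.00, unchanged |
| 15% vs 5% | about 0.50 → 0.54–0.55 | 1.00–1.01 → 0.90–0.91 |
| 28% vs 8% | about 0.50 → 0.59–0.60 | about 1.0 → 0.81–0.83 |
| 5% vs 15% | not reported | 1.00 → 1.11 |

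Rejection under the null (1,000 trials, Monte Carlo error about 0.7 points) moves from 4.6% to 5.5% at 15% versus 5%. It reaches about 8% only at 28% versus 8%.

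**Step 4: A second model**

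This uses events divided by time at risk, with median 30 months, 12–36 months of follow-up, and switch dates assigned uniformly between 2 and 18 months to the stated share of patients. With 20% versus 5% assigned a switch date, the null rate ratio goes from 1.01 to 0.91. With 5% versus 20% it goes from 0.99 to 1.10. With 10% in each arm it stays at 1.00, while the event rate falls to 0.935 of its value under the before-therapy rule.

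**The case against.** The strongest reply is that 6.2 is silent about later scans and does not admit them. A rule triggered by starting a therapy is naturally read as the last assessment before it. The literal reading is also awkward: a patient who switches and then has scan-documented progression would be censored at or after that scan. This stands as a reading of intent. A reader might infer that the SAP deliberately counts assessments of any date, and the text does not support that. It does leave a DOR programmer without the limiting words.

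A reader might also infer that PFS follow-up already stops at two different dates. Three explicit statements give one date, so PFS changes only if 6.2 is the rule programmed. PFS is outside the Hochberg family, and Protocol 11.10.2.1.6 plans no formal PFS test.

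A third tempting inference is a demonstrated bias toward Arm A. The documents do not support it:

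- They give no switching rates in either arm.
- Protocol 8.4.1 lets an Arm A patient who stops one drug continue the other, so stopping ublituximab need not lead to a new therapy.
- Assuming no progression after switching is the upper case, and the simulation includes no deaths after switching, whereas 6.2 counts death after stopping study drug as an event.
- If DOR is tested at the ORR analysis (at least 16 weeks of evaluation, 18–24 months of enrollment), follow-up of responders is nearer 2–26 months. The gain per switcher then falls from about 14.6 to about 9.5 months. The hazard ratio shift at 15% versus 5% is similar, and null rejection moves only from 4.4% to 5.0%.

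These points limit the size and direction of the effect. They do not remove the gap in the only DOR rule.

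**Conclusion.** The point holds as a conflict in the text that matters for DOR. Followed literally, 6.2 gives a later censoring date than the plan's own new-therapy rule whenever a scan follows the switch.

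No figure in the documents changes, and the actual size cannot be computed. The illustrations rest on assumed switching shares and on no progression being scored afterwards. On those terms the harm is mainly to the estimates. Moderately unequal switching moves a null hazard ratio by about 0.1, in favor of the arm that switches more. Equal switching lengthens DOR without moving the hazard ratio appreciably. Type I error changes little except in the extreme case.

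This should be corrected before database lock. It does not threaten the primary conclusion.

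**What to change.** In SAP 6.2, state that for both DOR and PFS any patient who starts alternative anti-tumor therapy before progression is censored at the last tumor assessment prior to the start of that therapy, including a patient who also meets the second bullet. Without that clause, someone who stops study drug and later switches could still be censored under the unrestricted wording.

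Carry only the new-therapy row of Table 3 over to DOR, with time measured from first documented response. The rest of Table 3 should not be imported wholesale, because its randomization-date rows and formula do not fit DOR. Leave the inclusion of NE assessments as it stands unless it is changed separately.

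The cost is one SAP sentence, with no new data, visits or patients. DOR may look slightly shorter, with slightly more early censoring.
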